## 9.2 Randomization

Subjects are assigned to a treatment group at the time the device is shipped to the subject. Assignments are made alternating between Group 1 and 2 until enrollment is complete.

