## 1.4 Interventions and Duration

Participants will self-administer electrical stimulation using the ELITONE-UUI device, 20-25 minutes per session, 4-5x per week, for 6 weeks. Participants will be randomly assigned to one of two groups, each group receiving a different device configuration wherein the stimulation frequency (e.g. 10Hz, 50Hz) differs between the groups. The ELTIONE-UUI device is identical to Elidah's ELITONE device, except for the digitally controlled stimulation parameters.

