## 2.3 Hypothesis

This case series is not a hypothesis driven study. The expectation is that both treatment groups will realize a clinically meaningful reduction (≥50%) in urinary incontinence episodes per day

relative to a pre-treatment baseline. Secondary measures may also show clinically meaningful changes. Differences between the groups may inform selection of a device configuration to move toward product commercialization.

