## 5.2 Number of Subjects

20 subjects per treatment group (40 total). Appreciating that some subjects who are initially enrolled will fail to complete treatment and return the study materials, it is likely that 50-55 subjects will be enrolled. See 9.1 for discussion of the sample size calculation.

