## 5.4 Protocol Schedule

The study comprises five stages: Pre-study, Baseline, Verification, Treatment, and Post-Study.

- Pre-Study –The subjects initiate pre-study activity, which includes completion of the I-QoL Questionnaire and the Pre-study Incontinence History. The subject submits the pre-study materials to Elidah (electronically or hardcopy).
- **Baseline** –Concurrently, the subjects maintain the Daily Log for 7 days to establish a baseline of the episodes/day and pads/day measures. No treatment is administered during this period. After 7 days the subjects submit the data to Elidah (electronically or hardcopy). Subjects are instructed that they should not perform baseline activity during menses or if they are ill. Note that it is acceptable to complete or return the Pre-Study materials throughout this 7 day baseline period.
- **Verification** If the 7 day Baseline shows that the subject does not qualify based on urinary incontinence episode exclusion criteria (<1/day, >5/day) then the subject will be disqualified and the device will not be sent. The subject will be notified of disqualification, or if qualified, will be sent a link for deposit payment/hold. Qualifying subjects will be randomly assigned to a treatment group and a corresponding ELITONE-UUI device will be mailed to them.
- Treatment Subjects will self-administer treatment with the ELITONE-UUI device. Subjects will treat 5x/week for six weeks. Each treatment is 20 minutes. No more than one treatment per day. See Section 6 and Table 5-1 for a detailed description of the device and treatment regimen. If subjects are ill or in menses during the 6th study week they are instructed to extend treatment for at least 5 days after menses and/or they are in good health. During the treatment weeks subjects are required to maintain their Daily Log. There is no difference in treatment requirements between the two treatment groups.
- Post-Study Upon completion of treatment subjects complete the post-study requirements, which include the I-QoL questionnaire and a post-study usability questionnaire. Subjects are requested to complete the requirements and return the study materials to Elidah within 3 days of completing treatment. There is no difference in post-study requirements between the two treatment groups.

Table 5-1: Schedule of Subject Activities/Requirements.

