These three analyses suggest a treatment group in the range of 12-31 subjects would be suitable for an RCT study. Taking a conservative approach, and appreciating that the proposed study is not an RCT design, Elidah will aim to enroll 20 subjects in each treatment group, for a total of 40 subjects. See 9.4 regarding interim analysis and stopping rules.

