# 9.5 Data Analyses

This is not a hypothesis driven study. Descriptive statistics will be the primary means of data analysis. Comparison between the treatment groups may be made to, in part, support Elidah's selection of a preferred configuration for eventual product commercialization. However, this case series study is not designed to allow rigorous statistical analysis between the groups.

Electrical stimulation is known to have a positive effect on both UUI, and some women have difficulty distinguishing between UUI and SUI episodes. Accordingly, in an effort accurately capture the totality any therapeutic improvement, the study's **primary outcome measure** of efficacy is a change in total urinary incontinence (UI) leaks, both SUI and UUI. Each adherent subject's Daily Log will be used to determine the average number of urinary incontinence episodes per day for the baseline and 6th week (see 5.5 regarding subject adherence). To accommodate the likelihood that some subjects will omit log data, the "weeks" referred to in the baseline and 6th week assessments refer to the first and last 5 entries in the Daily Log. The percent reduction in UI episodes is then calculated for each patient by subtracting the final week average from the baseline average, dividing the difference by the baseline average, and multiplying by 100. The percent reductions for each patient are then used to define an average (and standard deviation) reduction for each treatment group.

UI episodes per day data may additionally be reported as a responder rate. FDA guidance suggests that subjects with a percent reduction of  $\geq$ 50% be considered responders. Accordingly, the responder rate for each treatment group will be calculated by dividing the number of subjects with a reduction of  $\geq$ 50% by the total number of subjects.

**Secondary outcome measures** will similarly use descriptive statistics (e.g. mean, standard deviation) to characterize changes from baseline. Additionally, where applicable, FDA suggested response rate thresholds will be referenced. Notes on specific secondary outcome measures include:

- Change in urgency episodes with a leak UUI leak data will be analyzed in the same manner as the primary outcome measure data.

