# 9.6 Data Pooling

This study is, in part, being conducted to provide scientific evidence to support FDA clearance of the ELITONE-UUI device. Elidah may pool data from both treatment groups if there is demonstrated homogeneity between the subject groups and the outcome measures.

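### Sections 1.4 and 5.4 promise random assignment, but section 9.2 alternates the two groups at shipping, so the configuration comparison is not randomised

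*Combined protocol and SAP*

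**What the plan says.** Two sections describe random assignment. Section 1.4: "Participants will be randomly assigned to one of two groups". Section 5.4, under Verification: "Qualifying subjects will be randomly assigned to a treatment group". Section 9.2 is headed Randomization and sets the moment of assignment at device shipment. It then gives the rule: "Assignments are made alternating between Group 1 and 2 until enrollment is complete". No section mentions a random sequence, a list, blocking or concealment, or says which group comes first.

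The plan limits its own claims. Section 9.1 sets the sample size "appreciating that the proposed study is not an RCT design", and section 9.5 says that "this case series study is not designed to allow rigorous statistical analysis between the groups". It nevertheless gives the groups a purpose. Section 2.3: "Differences between the groups may inform selection of a device configuration to move toward product commercialization". Section 9.6: "Elidah may pool data from both treatment groups if there is demonstrated homogeneity between the subject groups and the outcome measures".

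On blinding, sections 5.7 and 6.4 treat the women as blinded to their group, while section 9.3 says that neither they nor the staff in contact with them are considered blinded. Section 5.7 agrees that study staff are unblinded.

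**The concern.** Strict alternation is systematic allocation. Choosing the first group at random, which the plan does not say it does, would leave every later assignment fixed.

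The practical worry is selection at the shipping step. By then the sponsor holds each woman's 7-day baseline log (5.4), so her severity is known. Staff know the groups (5.7), and the documents do not say who sets the shipping order. If several verified women are waiting, whoever orders the shipments could influence who receives which configuration.

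The stake is the comparison of configurations, which may feed a commercial choice (2.3, 9.5). A reader who relies on 1.4 or 5.4 would also report the comparison as randomised, which is inaccurate if 9.2 is followed. Pooling under 9.6 is a lesser matter, since it turns on how alike the groups are found to be.

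**Working it through.** The central finding is textual.

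| Section | Assignment |
|---|---|
| 1.4 | random, two groups |
| 5.4 | random, after the baseline check |
| 9.2 | alternating, at shipment |

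These cannot all be true, and only 9.2 gives a procedure. The plan states no figure on this point to reproduce. The calculations below measure predictability and the cost of a remedy, not harm.

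**Inputs.** Section 5.2 gives 20 per group, 40 in total, and says "it is likely that 50-55 subjects will be enrolled". The number of devices shipped is not stated. A woman becomes a subject at consent (4.3), before verification, so I assume 45 to 55 shipments. Completion rates are assumed from the plan's own figures: 40/50 = 80% and 40/55 = 72.7%. Completion is taken as independent of group.

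**Predictability at shipping.**
- Alternation, (n − 1)/n: 49/50 = 98.0%; 54/55 = 98.2%.
- One shuffled list of 56 entries, 28 per group, always guessing the group with more entries left (exact recursion): 55.4% correct over 50 shipments and 56.7% over 55.

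**Group sizes with the list.** The number in Group 1 among the first n entries is hypergeometric (56 entries, 28 in Group 1, n drawn), with SD √[n × ¼ × (56 − n)/55].
- n = 50: SD = √(12.5 × 6/55) = 1.17. P(each group has 23–27) = 0.977; the possible range is 22–28.
- n = 55: always 27 and 28.
- n = 45: P(each group has 20–25) = 0.960; P(one group below 20) = 0.040.

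**Simple randomisation.** With a binomial (n, ½) split, P(one group starts below 20) is 0.371 at n = 45, 0.119 at n = 50 and 0.030 at n = 55.

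**Chance that both groups reach 20 completers.** For a split a/b, this is P(Bin(a, p) ≥ 20) × P(Bin(b, p) ≥ 20), averaged over the possible splits.

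| Shipped, completing | Alternation | 28/28 list | Simple |
|---|---|---|---|
| 50, 80% | 0.380 | 0.335 | 0.195 |
| 55, 72.7% | 0.350 | 0.350 | 0.209 |

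For example, alternation at 50 gives 25/25, with P(Bin(25, 0.8) ≥ 20) = 0.617, and 0.617² = 0.380.

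**The case against.** The strongest reply is that this is a case series that disclaims a rigorous group comparison, with a within-woman primary outcome, so what remains is an inaccurate word in two places and a heading. That is right about the primary outcome and the ≥50% targets in 9.1: neither depends on how groups are formed. It does not justify leaving the word in. If no randomised comparison is intended, the text should say so.

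The route for steering is also thin. Eligibility is a numeric check, each woman must act on a deposit link before shipment (5.4), and enrolment is expected to take about a month (9.4). At consent her shipping slot is not yet fixed. All of this stands and makes the opportunity narrow. It does not close it, because nothing fixes the order among women who are ready to ship.

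Section 9.3 does blind the personnel who calculate individual results. That protects the calculation but does not conceal the next assignment.

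The pooling argument is weak: the same women enter the pool however they were split, and 9.6 requires homogeneity to be demonstrated. This largely stands, and the configuration choice carries the point.

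Finally, the completer probabilities treat 50 or 55 as a fixed total. If recruitment continues until each group has 20 completers, they do not apply. They serve only to show that a random list costs little balance.

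**Conclusion.** The concern holds and should be fixed. As written, the plan describes as random an allocation that its only stated method makes deterministic: at shipping, 49 of 50 or 54 of 55 assignments follow from the one before. This rests on the text of 1.4, 5.4 and 9.2 and needs no numerical assumption beyond the number shipped.

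The consequence is limited. The main efficacy results stand. The descriptive comparison of configurations loses the protection that the word *randomly* implies, and reporting it as randomised would be wrong. The size of any bias cannot be estimated from the documents, and nothing in them shows that bias would occur.

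The conflict over the women's blinding is real but separate. It affects how differences in self-reported outcomes between the groups should be read.

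**What to change.** **Preferred.** Replace the rule in 9.2 with one random 1:1 list generated in advance, for example 28 per group in a single shuffle, and longer if more than 56 devices may ship. It should be held by an existing staff member who neither verifies eligibility nor sets the shipping order. That person should not be the Clinical Director, who verifies eligibility (10.5), or an analyst whom 9.3 keeps blinded. Release each entry only after verification and deposit, and do not change it afterwards. The documents do not show whether such a person is available, so the sponsor must confirm this.

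The cost is a short amendment, the list, and slightly unequal groups. Under the assumptions above, the chance that both groups reach 20 completers falls from 38% to 34% at 50 shipped and stays at 35% at 55. Simple randomisation is less suitable at this size.

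**Minimum.** If alternation is kept or has already been used, delete *randomly* in 1.4 and 5.4, retitle 9.2 as Group assignment, and describe the comparison as non-randomised wherever it is reported. This needs only a wording change with IRB review (11.1), but gives up the randomised description.

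**Separately.** Reconcile 5.7 and 6.4 with 9.3, so that the women's blinding status is stated once and reported consistently.

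No change to sample size, endpoints or treatment follows from either option.

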# 9.3 Blinding

The instructional materials provided to each subject will include a brief description of the waveform (e.g. 4 seconds with one stimulation, followed by 4 seconds of a slightly different stimulation, followed by 6 seconds of rest), which aides is establishing expectations of proper function and identification of a suitable treatment intensity. Accordingly, the subjects and staff members interacting with those subjects are not considered to be blinded.

Study personnel responsible for post-treatment data analysis will be blinded from the group assignment during analysis of individual subject data. For example, baseline and 6th week episodes/day calculations and pad weight measurements will be made for each subject without knowledge of group assignment.

## 9.4 Interim Analyses and Stopping Rules

Due to the short duration of the study (6 weeks) and likely rapid enrollment (1 month), there are no plans for an interim analysis.

In the event of a serious adverse event related to the device/treatment the study will be halted until the safety issue can be addressed (see 7). Due to the small enrollment size, a pre-specified number of adverse events will not be used to trigger an early end to the study.

\_

<sup>2 Richardson et al, "Pelvic floor electrical stimulation: A comparison of daily and every-other-day therapy for genuine urge incontinence", Adult Urology, 48(1):110-118, 1996.

# 9.5 Data Analyses

This is not a hypothesis driven study. Descriptive statistics will be the primary means of data analysis. Comparison between the treatment groups may be made to, in part, support Elidah's selection of a preferred configuration for eventual product commercialization. However, this case series study is not designed to allow rigorous statistical analysis between the groups.

Electrical stimulation is known to have a positive effect on both UUI, and some women have difficulty distinguishing between UUI and SUI episodes. Accordingly, in an effort accurately capture the totality any therapeutic improvement, the study's **primary outcome measure** of efficacy is a change in total urinary incontinence (UI) leaks, both SUI and UUI. Each adherent subject's Daily Log will be used to determine the average number of urinary incontinence episodes per day for the baseline and 6th week (see 5.5 regarding subject adherence). To accommodate the likelihood that some subjects will omit log data, the "weeks" referred to in the baseline and 6th week assessments refer to the first and last 5 entries in the Daily Log. The percent reduction in UI episodes is then calculated for each patient by subtracting the final week average from the baseline average, dividing the difference by the baseline average, and multiplying by 100. The percent reductions for each patient are then used to define an average (and standard deviation) reduction for each treatment group.

UI episodes per day data may additionally be reported as a responder rate. FDA guidance suggests that subjects with a percent reduction of  $\geq$ 50% be considered responders. Accordingly, the responder rate for each treatment group will be calculated by dividing the number of subjects with a reduction of  $\geq$ 50% by the total number of subjects.

**Secondary outcome measures** will similarly use descriptive statistics (e.g. mean, standard deviation) to characterize changes from baseline. Additionally, where applicable, FDA suggested response rate thresholds will be referenced. Notes on specific secondary outcome measures include:

- Change in urgency episodes with a leak UUI leak data will be analyzed in the same manner as the primary outcome measure data.
- Change in urgency episodes without a leak Differences in mobility, activity, etc. may impact whether a subject can get to a toilet before an urgency leak occurs. Analysis of episodes without leaks will occur in the same manner as the "with leak" data.
- Change in pad use Reduction in pad usage will be assessed as a percent change relative to the baseline, and as a response rate, wherein a 50% reduction is considered clinically significant. Subjects who do not use a pad during the baseline week will be excluded from the analysis.
- Change in daily bathroom visits / Change in nighttime bathroom visits Descriptive statistics as defined above.
- I-QoL Incontinence Quality of Life scores will be analyzed with respect to a change from baseline. Responders will be those with an I-QoL score increase of 2.5 points, which is defined in the FDA guidance as clinically significant.

Usability surveys will solicit subject feedback pertaining to their experience with the product. Appropriate statistical methods will be used in reporting these subjective measures.

In addition to characterizing outcome measures as a change in value/score (i.e. percent reduction) or a clinically meaningful response (e.g. ≥50% change), post hoc analyses may investigate outcome measures using analysis of covariance (ANCOVA), wherein baseline values are modeled as covariates, which has the advantage of accounting for variation in the magnitude

of the baseline. Additional post hoc ANCOVA may be performed with covariates including age, type of incontinence, BMI or other potentially relevant variables.

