## 2.2 Primary Endpoint

Treatment efficacy is assessed by comparing the average number of urinary incontinence episodes per day at the end of treatment to the corresponding pre-treatment number.

Safety is determined by review of Adverse Events as defined in 7.3, and determination of no serious adverse event during the study.

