#### Recruitment

\* During the baseline week subjects will be excluded if they average less than 1 urge incontinence episode per day (with or without a leak).

- Ads placed in social media and other forums to attract candidates to a website that describes the study. These ads will be places in the US without regional geographic targeting and use key words including "incontinence" and "bladder leaks"
- Email to a list of women with urge incontinence who had previously expressed interest in participating in a clinical study.
- Alternately, healthcare providers who become familiar with the study can direct candidates
  to the study. These candidates will go through the same screening as all candidates and
  the referring healthcare provider would not be considered a study investigator. It is
  permissible for the referring healthcare provider to assist the candidates with completion
  of screening/consent information and to forward the information to Elidah.
- TR-1155-FORM-14 identifies the language that will be used in recruitment messaging.

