#### 5.5 Adherence Assessment

Adherence to the study regimen for the active group requires completion of ≥20 of the 30 prescribed treatment sessions, as determined from review of each subject's Daily Log and the device's memory.

Further, subjects must complete the Pre-study, Baseline and Post-Study requirements to be considered compliant. If a subject does not adhere to the study requirements they will be asked to provide a reason, which will be documented in the Case Report Form (TR-1155-FORM-10). During data analysis, this information will be reviewed by the Data Safety and Monitoring Board to determine if/how the data should be adjudicated (see 10.5).

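### The primary percent reduction divides by the first 5 log entries, although 5.4 establishes and checks the baseline on 7 days, so collected baseline days are discarded without need

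*Combined protocol and SAP*

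**What the plan says.** Section 5.4 (Protocol Schedule) states that "the subjects maintain the Daily Log for 7 days to establish a baseline of the episodes/day and pads/day measures". The log is submitted after those 7 days. The verification step opens with "If the 7 day Baseline shows that the subject does not qualify based on urinary incontinence episode exclusion criteria", with limits of below 1 and above 5 per day, and a woman who fails it is sent no device.

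Section 9.5 (Data Analyses) defines the primary measure for each adherent woman as baseline average minus final-week average, divided by the baseline average, times 100. It expects some log entries to be omitted, and for that reason says that the weeks "referred to in the baseline and 6th week assessments refer to the first and last 5 entries in the Daily Log". Complete logs are not excepted. Urgency episodes with and without a leak are analysed in the same way.

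For the final value, 2.2 speaks of "comparing the average number of urinary incontinence episodes per day at the end of treatment to the corresponding pre-treatment number", while 9.3 and 9.5 call it the 6th week. Under 5.4, women who are ill or in menses in that week have an extension: "they are instructed to extend treatment for at least 5 days after menses and/or they are in good health". Table 5-1 has a key for endpoint data and appears to mark the Daily Log that way at weeks 0, 6 and 7 only (the symbols are read from extracted text). Section 5.5 sets adherence at "completion of ≥20 of the 30 prescribed treatment sessions" plus the pre-study, baseline and post-study requirements. It does not name a week-6 log.

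**The concern.** The protocol has two baselines: 7 days for entry and 5 entries for efficacy. The efficacy baseline is the denominator of a ratio. Shortening it adds noise to every woman's percent reduction and, because dividing by a noisy quantity is not symmetric, also pulls the group mean down. Days 6 and 7 have already been collected and reviewed by then, so the loss buys nothing. With about 20 women per group and a purely descriptive analysis, the mean and SD are the result. Section 9.1 sets them beside an expected reduction of at least 50%.

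The final value raises a smaller question. If the last 5 entries can come from before week 6, a result labelled 6th week may partly describe earlier weeks, and the plan does not say for how many women.

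**Working it through.** The plan gives no figure for this point. The documents give no daily variance or day-to-day correlation, so all sizes below rest on stated assumptions.

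**1. Days lost.** Days discarded = logged baseline days minus 5, or zero if that is negative: 7 logged loses 2 (29%), 6 loses 1, 5 loses none. With fewer than 5, the first 5 entries would run into treatment days, unless the 5.5 baseline requirement removes the woman.

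**2. Precision of the baseline mean.** With independent days, SE(5)/SE(7) = √(7/5) = 1.18. The 7-day SE is 1/1.18 = 0.845 of the 5-entry SE.

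**3. Two worked logs.**
- Baseline 3, 3, 2, 2, 2, 1, 1 with final mean 1.2. Five entries: 12/5 = 2.4, reduction (2.4 − 1.2)/2.4 = 50%, a responder. Seven days: 14/7 = 2.0, reduction 40%, a non-responder.
- Baseline 1, 1, 1, 1, 1, 3, 3 with final mean 0.6. Five entries: 1.0, reduction 40%. Seven days: 11/7 = 1.57, reduction 62%.

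**4. Eligible on 7 days, below 1/day on 5.** Given T episodes in 7 independent days, the first-5 total is binomial(T, 5/7), and a mean below 1/day needs a total of 4 or less. T = 7 gives 32%, T = 8 gives 17%, T = 10 gives 3.8%, T = 14 gives 0.1%.

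**5. Simulation of the primary measure.** Assumptions: women's true means gamma-distributed (shape 2, 4 or 8) with mean 2.0 or 2.5 leaks/day; daily counts Poisson, or negative binomial with variance twice the mean; eligibility on a 7-day leak mean of 1-5; final window 5 days; true reduction 50%; independent days; 200,000 women per scenario.

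| | 5 baseline entries | 7 baseline days |
|---|---|---|
| SD of percent reduction (points) | 30.5-53.0 | 26.1-39.1 |
| SE for 20 women (SD/4.47) | 6.8-11.9 | 5.8-8.7 |
| Mean percent reduction | 41.9-47.7 | 45.9-49.6 |

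Within scenarios the SD ratio is 0.74-0.86, so the SD falls by 14-26%. The 7-day mean is 1.7-4.6 points nearer 50. At a true 72% reduction the gap in means is 1.0-2.5 points.

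**6. Less favourable assumptions.**
- Real differences in response (SD of true reductions 20-30 points): total SD 38.0-65.1 against 33.7-51.3, 9-24% lower.
- Eligibility by the 4.2 footnote, which counts urge episodes with or without a leak, and day-to-day correlation 0.7: SD ratio 0.92-0.985, only about 2-8% lower.
- Every woman at a true rate of exactly 1/day, the eligibility edge: selection lifts both means above 50 (56.6 against 59.2, Poisson), and there the 5-entry mean is the nearer one.

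**7. Responders.** Over all true-50% scenarios with mixed true rates, the 5-entry rule gives a rate 0.4-3.3 points higher, less than one woman in 20 (5 points). About 10% of women change label, roughly 2 of 20, but the changes largely cancel. With every woman at one fixed rate (1-4/day), the net shift ran from about −1 to +6 points, largest at 1/day.

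**8. Final value.** At 5 sessions a week, 20/5 = 4 weeks, so 20 sessions can be reached by day 28. A log ending there gives days 24-28; a complete log gives days 38-42. If the effect has levelled off by week 4, the shift is 0. If it grows linearly to 50% at week 6, week 4 shows 50 × 4/6 = 33.3, a shortfall of 16.7, and one such woman moves a group mean of 20 by 16.7/20 = 0.83 points. Both paths are assumptions.

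**The case against.** The 5-entry rule is deliberate, pre-specified and reasoned, and gives equal windows at both ends. The study is descriptive, so no test loses power. The gap in means is smaller than the standard error of a 20-woman group even after the change. These points stand and limit the weight of the finding. They do not defend the rule: a mean of all logged baseline days meets the same missing-data need, and in none of the scenarios run did discarding days improve precision.

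Four stronger readings are tempting, and the documents do not support them.

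- *Two days are always lost.* This happens only when all 7 are logged.
- *A 7-day denominator guarantees at least 1 leak a day.* It does so only if eligibility is judged on leaks. By the 4.2 footnote, "subjects will be excluded if they average less than 1 urge incontinence episode per day", leak or no leak, so the 7-day leak mean could also fall below 1.
- *The rule favours the sponsor.* In the mixed-population scenarios it lowers the mean and slightly raises the responder rate, so there is no single direction.
- *The final window is undefined, so the 6th-week result is biased.* The last-5 rule fits the end-of-treatment wording of 2.2, and Table 5-1 appears to point to weeks 6 and 7. Section 4.5 has staff monitor the diary every two weeks, and section 8 lists log lapses and missed treatment as possible grounds for discontinuation. That ground is discretionary and 9.5 does not invoke Table 5-1, so a gap remains. Nothing shows how many women fall into it.

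**Conclusion.** The baseline point holds. For any woman with more than 5 logged baseline days, 9.5 discards data that 5.4 collects for exactly this purpose. Under the main assumptions (mean 2-2.5 leaks/day, variance 1-2 times the mean, independent days, true 50% reduction, eligibility on leaks), all 7 days give a 14-26% smaller noise SD and a mean 1.7-4.6 points nearer the truth. The SD gain is 9-24% with real differences in response and may be only 2-8% with footnote eligibility and strongly correlated days. The effect on the group responder rate is at most about 3 points in realistic mixes of baseline rates. This is a modest but nearly free improvement, not a flaw that invalidates the study.

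The final-value point is secondary, and mainly one of labelling and reconciliation. A woman who reaches 20 sessions by week 4, stops logging and completes the post-study forms could have earlier data reported as 6th week. The number affected and the direction of any bias are unknown.

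**What to change.** In 9.5:

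1. Define baseline as the mean of all logged days in the 7-day pre-treatment period, never treatment days. State a minimum number of days and what happens to a woman below it. Apply this to the primary measure and to the log measures analysed the same way.
2. Report the current 5/5 result as a sensitivity analysis.
3. Keep the last 5 entries as the final value, label it end of treatment (last 5 entries), and reconcile that definition with Table 5-1 and the 6th-week wording in 9.3 and 9.5.
4. If log entries are dated, report per group how many women have any of those 5 entries before week 6.

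The cost is about one paragraph. Items 1 and 2 need no new data, because the baseline log is submitted before the device is sent. Item 4 needs a date or day number on each entry; the Daily Log form is a separate document, and the protocol text does not say whether it has one. The drawback is unequal windows, up to 7 days against 5, which the 5/5 sensitivity analysis covers.
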